[figure not shown]
[figure not shown]

## CLINICAL TRIAL PROTOCOL SYNOPSIS

Company name	Boehringer Ingelheim
Protocol date	31 Mar 2020
Revision date	23 Jun 2022
BI trial number	1368-0024
Title of trial	An open-label, single arm, long term trial of Spesolimab treatment in patients with Palmoplantar Pustulosis (PPP) who have completed previous BI Spesolimab trials
Coordinating Investigator	 Tel.:  Fax: 
Trial site(s)	Multi-centre trial
Clinical phase	II
Trial rationale	Evaluate long term safety and efficacy in patients with Palmoplantar Pustulosis; Offer patients with a health benefit in the parent trials to continue Spesolimab (BI 655130) treatment with the aim to maintain their health benefit;
Trial objective(s)	1) To evaluate the long-term safety of Spesolimab (BI 655130) in patients with PPP, who have completed previous Spesolimab (BI 655130) trials and are qualified for entry in this trial. 2) To evaluate the long-term efficacy of Spesolimab (BI 655130) in patients with PPP, who have completed treatment in previous Spesolimab trials and are qualified for entry in this trial.
Trial endpoints	Primary endpoint is the occurrence of treatment emergent adverse events (TEAEs) up to week 260 of maintenance treatment  Secondary endpoints are 
 
- Percent change in PPP ASI from baseline in parent trial at week 48, 96, 144, 192, 240 and 260
 
- Proportion of patients with PPP ASI50 compared to baseline in parent trial at week 48, 96, 144, 192, 240 and 260
 
- Proportion of patients with PPP PGA of 0 (clear) or 1 (almost clear) at week 48, 96, 144, 192, 240 and 260
 

Trial design	Open label (OL), 5 years treatment, single arm, long-term extension trial
Total number of patients randomised	No randomisation, 500 patients from parent trial expected

Number of patients on each treatment	Only one open label dose, 500 patients from parent trials expected
Diagnosis	Palmoplantar Pustulosis
Main in- and exclusion criteria	

• Willing male or female patients who have completed treatment in one of the parent trials without premature discontinuation

• Patients who have obtained an individual health benefit, per investigator judgement (such as PPP PGA of 0 (clear) or 1 (almost clear) or other clinical improvement), from treatment in the parent trial.

• Women of childbearing potential (WOCBP) must be ready to use highly effective methods of birth control

• Patients who experienced study treatment-limiting adverse events during their pre-ceding trial are to be excluded.

Test product(s)	Spesolimab, BI 655130
dose	600 mg every 4 weeks
mode of administration	subcutaneous (s.c.)
Comparator product(s)	Not applicable
dose	Not applicable
mode of administration	Not applicable
Duration of treatment	260 weeks
Statistical methods	Descriptive statistics only

## FLOW CHART VISIT 1-15

Please see also footnotes at the very end of the Flow Chart table.

Trial Periods	Screening	Maintenance Treatment													
		2 	3	4	5	6	7	8	9	10	11	12	13	14	15
Visit	1 	2 	3	4	5	6	7	8	9	10	11	12	13	14	15
Week	N/A	0	4	8	12	16	20	24	28	32	36	40	44	48	52
Day	-28 to -1	1	29	57	85	113	141	169	197	225	253	281	309	337	365
Visit Window (days)	N/A	±7	±7	±7	±7	±7	±7	±7	±7	±7	±7	±7	±7	±7	±7
Informed consent	X 														
Review of in-/exclusion criteria	X														
Demographics	X														
Baseline conditions, Medical History	X														
Infection Testing 	X 														X
Physical examination 	X C,1					X T				X T					X C
Vital signs 	X 	X	X	X	X	X	X	X	X	X	X	X	X	X	X
Smoking status / history 	X														X
12 lead-ECG 	X 														X
Pregnancy test 	X 1,U,(S)	X U,(S)	X U,(S)	X U,(S)	X U,(S)	X U,(S)	X U,(S)	X U,(S)	X U,(S)	X U,(S)	X U,(S)	X U,(S)	X U,(S)	X U,(S)	X U,(S)
Safety laboratory tests 	X 					X				X					X
[REDACTED]		■				■				■					■
[REDACTED]		■				■				■					■
[REDACTED]		■				■				■					■
[REDACTED]	■					■				■					■
PPP PGA, [REDACTED]	X 					X				X					X
PPP ASI, [REDACTED]	X 					X				X					X
[REDACTED]	■					■				■					■
[REDACTED]	■					■				■					■
IRT Call	X	X	X	X	X	X	X	X	X	X	X	X	X	X	X
Administer trial drugs 		X	X	X	X	X	X	X	X	X	X	X	X	X	X
Local tolerability 		X	X	X	X	X	X	X	X	X	X	X	X	X	X
Concomitant therapy	X	X	X	X	X	X	X	X	X	X	X	X	X	X	X
Adverse Events 	X	X	X	X	X	X	X	X	X	X	X	X	X	X	X
Study Completion															

**FLOW CHART VISIT 16-EOS**

Trial Periods	Maintenance Treatment													Follow-up	
	16	17	18	19	20	21	22	23	24	25	26	27-66	67/ EoT		68/EoS 
Visit															
Week	56	60	64	68	72	76	80	84	88	92	96	Repeat every 4 weeks until EoT	260	16wks after the last trial drug administration	
Day	393	421	449	477	505	533	561	589	617	645	673		1821		
Visit Window (days)	±7	±7	±7	±7	±7	±7	±7	±7	±7	±7	±7	±7	±7	+7	
Informed consent															
Review of in-/exclusion criteria															
Demographics															
Baseline conditions, Medical History															
Infection Testing 											X	X 	X		
Physical examination 			X T				X T				X C	X T,19	X C	X C	
Vital signs 	X	X	X	X	X	X	X	X	X	X	X	X	X	X	
Smoking history/status											X	X 	X	X	
12 lead-ECG 											X	X 	X	X	
Pregnancy test 	X U, (S)	X U, (S)	X U, (S)	X U, (S)	X U, (S)	X U, (S)	X U, (S)	X U, (S)	X U, (S)	X U, (S)	X U, (S)	X U,(S)	X U,(S)	X U,(S)	
Safety laboratory tests 			X				X				X	X 	X	X	
[REDACTED]			X				X				X		X	X	
[REDACTED]			X				X				X		X	X	
[REDACTED]			X				X				X		X	X	
[REDACTED]			X				X				X		X	X	
PPP PGA, [REDACTED]			X				X				X	X 	X	X	
PPP ASI [REDACTED]			X				X				X	X 	X	X	
[REDACTED]			X				X				X		X	X	
[REDACTED]			X				X				X		X	X	
IRT Call	X	X	X	X	X	X	X	X	X	X	X	X	X		
Administer trial drug 	X	X	X	X	X	X	X	X	X	X	X	X	X		
Local tolerability 	X	X	X	X	X	X	X	X	X	X	X	X	X	X	
Concomitant therapy	X	X	X	X	X	X	X	X	X	X	X	X	X	X	
Adverse Events 	X	X	X	X	X	X	X	X	X	X	X	X	X	X	
Study Completion														X	

Visit V1 of this long-term extension study should be performed during the last treatment visit (EoT) of the preceding parent trial of Spesolimab (BI 655130). This is strongly recommended.

Assessments done at the EoT-visit in the parent trial do not have to be repeated for Visit V1 in this extension trial. In case it is not possible to perform V1 of the extension trial at the EoT visit of the parent trial, the maximum days allowed between EoT parent trial and V1 of this trial will be 28 days. The time window for Visit 1 may be extended at the discretion of the Clinical Trial Leader on a case by case basis.

Even in this case the procedures of V1 that were already performed at EoT of the parent trial will not be repeated if there are no clinically significant changes in PPP and clinical status of the patient.

**Important:** results of lab or any other assessment that needs to be repeated in the opinion of the investigator must be available prior to V2 (1st IMP administration in the extension trial

See [Section 6.2.1](#) for detailed instructions.

V2 (= 1st IMP administration in extension trial) must be performed on Day 28 ( $\pm 7$ ) from EoT of parent trial (last IMP administration). The time window between last IMP administration in the parent trial and the first IMP administration in the extension trial may be extended in exceptional cases at the discretion of the Clinical Trial Leader on a case by case basis.

For patients who discontinue study medication in the extension trial before their scheduled end of treatment, an early EoT visit has to be scheduled. Subsequently EoS visit 16 weeks after the last dose of study medication has to be performed.

The written informed consent (IC) must be obtained prior to performing any study related procedures. Date of IC will be reported in the eCRF.

Infection testing at screening includes tuberculosis (TB), hepatitis B (HBV), hepatitis C (HCV), and HIV assessments. In patients with negative TB result, repeat the test approx. once a year at visits in Wk48, 96, 144, 192, 240 and at EoT, as long as the TB result is negative. HBV (not HCV and HIV) to be repeated at EoT.

For details on infection testing please see [Section 5.2.3](#) incl. table and important footnotes. See [Section 3.3.4.3](#) for newly occurring infections during the trial.

Physical examination: C=complete incl. weight, T=targeted (focus on evaluation of organ systems associated with AE(s) symptoms or laboratory abnormalities). For details please see [Section 5.2.1](#)

Measurement of vital signs should precede blood sampling and will be assessed pre-dose at all dosing visits and at approx. 10 minutes after study drug administration. For details please see [Section 5.2.2](#)

ECG measurements should always precede blood sampling and drug administration. ECGs are taken approximately once a year: at screening (not to be repeated if done at EoT in parent trial) and at visits in Wk 48, 96, 144, 192, 240, EoT and EoS; For details please see [Section 5.2.4](#)

[figure not shown]
Pregnancy testing is applicable only for women of childbearing potential (WOCBP).

U - urine pregnancy tests will be performed at all visits. Urine pregnancy testing should be done locally on-site prior to administration of study drug by using the urine-dipstick test provided by central lab. Study drug should only be administered in case of a negative test result. In case of a positive urine test result, the visit will be re-scheduled, IMP administration postponed and serum pregnancy test performed.

(S) - in case of a positive urine pregnancy test, a serum pregnancy test will be done and evaluated by the central lab. In case of a positive serum test, the patient must be discontinued from the trial. In case

of a negative serum test the trial team should be contacted to discuss if the previous visit can still be re-scheduled or must be skipped.

Includes clinical chemistry, hematology, coagulation and urinalysis assessments. Patient is not required to be fasting prior to blood collection but information on food before blood collection must be collected. At visits with study drug administration blood sampling should be done prior to the study drug administration. **TSH and HbA1c to be done at screening (not done at EoT in parent trial) and approximately yearly thereafter** in Wk48, 96, 144, 192, 240 and at EoT . Please see [Section 5.2.3](#) for details.

First study drug administration will be administered at V2 after eligibility criteria are confirmed. Administration of the study drug must be performed by a healthcare professional. Drug will be administered after PPP assessments. For the sequence of procedures please see [Section 6.2](#).

Local tolerability will be assessed during the study drug administration on site and retrospectively by asking the patient if local tolerability related AEs occurred. Please see [Section 6.2.2](#) for details.

After a patient's EoS-visit in the extension trial the investigator does not need to actively monitor the patient for new AEs but should only report new malignancies or the exacerbation of existing malignancies, trial treatment related SAEs and trial treatment related AESIs of which the investigator may become aware of by any means of communication. See [Section 5.2.6.2.2](#) for details.

 Please see [Section 5.2.6.2.1](#) for important instructions regarding AE collection in parent and extension trial.

Repeat every 16 weeks, at EoT and EoS

Current smoking status needs to be completely re-assessed at V1 of extension trial. Afterwards changes in smoking should be evaluated approximately once per year at visits in Wk 48, 96, 144, 192, 240, EoT and EoS;

[REDACTED]

[REDACTED]

[figure not shown]
[figure not shown]

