Malignancies	
Inhibition of the immune response with an immune-modulating biologic may increase the risk of a decreased immune defense against malignancies.
 
A recent characterisation of individuals with homozygous IL36R KO mutations revealed that normal immune function was broadly preserved suggesting that IL36 signalling pathway inhibition does not compromise host defences. [R17-3632].
	
Patients with a recent history of malignancy other than appropriately treated basal cell carcinoma or squamous cell carcinoma of the skin or in situ carcinoma of uterine cervix will be excluded from participation in this trial.
 
In case of occurrence of malignant neoplasm other than appropriately treated basal cell carcinoma or squamous cell carcinoma of the skin or in situ carcinoma of uterine cervix, the investigator should discontinue treatment with Spesolimab (BI 655130).
 
Diagnostics and treatment have to be initiated according to local standard of care.
 
Malignancies represent always serious adverse events and are subject to close monitoring

Table 1.4.2: 1 Risks (cont.)

Hypothetical risks of clinical relevance for this trial	Summary of data, rationale for the risk	Mitigation strategy
Trial procedures		
Blood Sampling	As with all blood sampling, there is a risk of mild pain, local irritation, or bruising (a black or blue mark) at the puncture site. Furthermore, there is a small risk of light-headedness and/or fainting. In rare cases, the puncture site can also become infected or nerves may be damaged, inducing long-lasting abnormal sensations (paresthesia), impaired sensation of touch and persistent pain.	These risks will be addressed by careful safety monitoring and risk mitigation measures such as (a) close clinical monitoring for AEs; (b) selection of experienced sites and site staff; (c) training.

Based on the findings in the nonclinical studies conducted to date and in accordance with international regulatory guidelines, the inclusion of Women of Child Bearing Potential (WOCBP) in this study is justified. To minimize the risk of unintentional exposure of an embryo or fetus to the investigational drug, WOCBP must agree to the requirements for the pregnancy testing and contraceptive methods as described in [Section 4.2.3](#).

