### 5.2.1 Physical examination

A complete physical examination incl. weight measurement will be performed at the time points specified in the Flow Chart. It includes at a minimum general appearance, neck, lungs, cardiovascular system, abdomen, extremities, and skin.

Targeted physical examination without weight measurement will include vital sign assessment and evaluation of organ systems associated with AE(s) symptoms or laboratory abnormalities.

The results must be included in the source documents available at the site.

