#### **6.2.2 Treatment period**

The treatment period lasts from Visit 2 (Day 1) until the End of Treatment Visit inclusively (EoT/Day 1821).

Study related procedures during treatment period will be performed as specified in the Flow Chart. Review also the notes at the end of the Flow Chart, they include important information regarding time points and important aspect to consider.

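### For a patient who stays on treatment, no complete physical examination is scheduled between week 96 and week 260 (164 weeks), although several other safety assessments stay yearly

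*Protocol*

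**What the plan says.** The protocol distinguishes two examinations. Section 5.2.1 gives the complete one a fixed content: "It includes at a minimum general appearance, neck, lungs, cardiovascular system, abdomen, extremities, and skin", together with weight. Of the other type it says: "Targeted physical examination without weight measurement will include vital sign assessment and evaluation of organ systems associated with AE(s) symptoms or laboratory abnormalities". Footnote 6 of the flow chart defines that type as "T=targeted (focus on evaluation of organ systems associated with AE(s) symptoms or laboratory abnormalities".

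Timing is left to the flow chart. It shows a complete examination at screening, at the end of year 1, at week 96, at EoT (week 260) and at EoS, with targeted examinations at weeks 16, 32, 64 and 80. The combined column for Visits 27-66 carries only the targeted code with footnote 19: "Repeat every 16 weeks, at EoT and EoS". Section 6.2.2 repeats the 16-week frequency and refers back to the flow chart and Section 5.2.1.

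Four other assessments keep yearly time points in that same stretch. Footnote 8 says "ECGs are taken approximately once a year" and lists them: "at visits in Wk 48, 96, 144, 192, 240, EoT and EoS". Footnotes 5 (TB), 10 (TSH and HbA1c) and 20 (smoking) also name weeks 144, 192 and 240. On cancer risk, the risk table in Section 1.4.2 states: "Malignancies represent always serious adverse events and are subject to close monitoring".

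**The concern.** The primary endpoint is the occurrence of TEAEs up to week 260. Physical examination feeds it directly. Section 5.2.6.1.1 requires clinically relevant examination changes to be recorded as AEs, and SAP Section 5.4.1 captures examination results only as baseline conditions or AEs. How systematically patients are examined therefore affects what enters the endpoint.

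Up to week 96 every patient is looked over about once a year, whether or not anything has been reported. After that, the scheduled examination is steered by symptoms and laboratory results. Skin, neck and abdomen need not be examined in a patient who reports nothing and has unremarkable laboratory values. The PPP ASI and PPP PGA continue, but they score palms and soles only.

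This matters most for slow, initially silent findings, which a 5-year extension is well placed to detect. SAP Section 7.8.1 reports malignant skin tumours, melanoma and non-melanoma skin cancer as separate categories, yet no general skin examination is required for more than three years. In the exposure-adjusted rate, a missed event is absent from the numerator while the patient keeps adding time at risk. An event dated late adds extra event-free time.

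**Working it through.** The plan gives no figure to reproduce; the check is schedule arithmetic from the flow chart.

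**Inputs.** Week 96 is Day 673 (Visit 26). Week 260 is Day 1821 (Visit 67/EoT), and Section 6.2.2 confirms it: "The treatment period lasts from Visit 2 (Day 1) until the End of Treatment Visit inclusively (EoT/Day 1821". Visits are 4 weeks apart from Visit 2 (week 0), with a window of ±7 days.

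**Calendar.** Day = 7 × week + 1. Week 96: 7 × 96 + 1 = 673. Week 260: 7 × 260 + 1 = 1821. Both match.

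**Weeks covered by the combined column.** Week = 4 × (visit - 2). Visit 27: 4 × 25 = 100. Visit 66: 4 × 64 = 256.

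**Gap between complete examinations.**
- 1821 - 673 = 1148 days; 1148 / 7 = 164 weeks
- 1148 / 365.25 = 3.14 years
- 164 / 260 = 63% of the treatment period
- with both visit windows: 1148 ± 14 = 1134 to 1162 days

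**Examinations inside the gap.** Every 16 weeks from week 96: weeks 112, 128, 144, 160, 176, 192, 208, 224, 240 and 256, which is 10, all targeted.

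**Comparison with the first 96 weeks.** The sequence is T, T, C, T, T, C. If the year-1 complete examination is at week 48, the intervals are 48 and 48 weeks. In the table as extracted it stands under week 52, which would make them 52 and 44. This may be an extraction artefact and does not change the 164 weeks.

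**Does other text fill the gap?** No. Section 5.2.1 refers to the flow chart for timing, and Section 6.2.2 gives only the 16-week frequency.

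**Would the earlier pattern fit?** Yes. Continuing T, T, C from week 96 puts the complete examination at weeks 144, 192 and 240. All three are among the 10 examinations already scheduled, and they are the weeks named for ECG, TB, TSH/HbA1c and smoking. The intervals would become 144 - 96 = 48, 192 - 144 = 48, 240 - 192 = 48 and 260 - 240 = 20 weeks, so the longest after week 96 falls from 164 to 48.

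**The case against.** The best defence is that a lighter schedule after two years is a legitimate design choice and that much surveillance continues. During weeks 100 to 256, AEs, vital signs and local tolerability are assessed every 4 weeks, safety laboratory tests every 16 weeks and ECG yearly. Unscheduled visits are allowed, and an independent DMC reviews safety data. The risk table calls the listed risks hypothetical and does not promise periodic examinations. No two passages contradict each other. All of this stands. It narrows the point without removing it, because these channels mostly depend on a symptom or a laboratory signal and none requires a general examination of a symptom-free patient who stays on treatment.

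Four stronger readings are tempting, and the documents do not support them:

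- *The targeted examination is confined to AEs already known.* The definition speaks of a focus and includes laboratory abnormalities, and Section 5.2.1 adds vital signs. In the sequence recommended in Section 6.2, AE collection precedes the examination, so a complaint first raised that day can direct it.
- *The complete examination is the only assessment that loses its yearly occurrence.* Six redacted flow chart rows have entries up to week 96, none for Visits 27-66, and entries again at EoT. Their schedule cannot be judged.
- *Silent findings would emerge only at EoT.* They may be noticed earlier by any of the routes above. Patients who stop early have an early EoT visit, and the EoT and EoS columns both show a complete examination.
- *A planned analysis would show a falsely low rate in years 3 to 5.* The SAP plans no year-by-year comparison. AEs are summarised over the whole maintenance period, descriptively and in a single arm.

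The loss of weight data also has little analytic consequence: in the visible SAP, weight serves only for baseline BMI.

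**Conclusion.** The point holds in a limited form. For a patient who remains on treatment, the plan schedules no complete examination, and hence no weight measurement, for 164 weeks (63% of the treatment period). It gives no reason for ending the roughly yearly pattern, although at least four other assessments keep theirs. Findings without symptoms or laboratory signals may be recorded late or missed, which weakens ascertainment of the 5-year TEAE endpoint and sits poorly with the stated close monitoring of malignancies.

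The size given is that of the schedule gap, not of a bias. The documents hold no data from which to estimate how many events would be missed or delayed. The conclusion assumes that the Visits 27-66 entry is complete as printed and that sites carry out what is scheduled and no more. That the break is an oversight, arising when 40 visits (66 - 27 + 1) were merged into one column, is plausible but is an inference. The point does not threaten the validity of the trial; it is a worthwhile and inexpensive correction.

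**What to change.** Reconcile the physical examination entry for Visits 27-66 with the plan's own yearly time points. Mark the examinations already scheduled at weeks 144, 192 and 240 as complete (C) and leave the other seven 16-weekly ones targeted. Align footnotes 6 and 19 and Section 6.2.2, so that the type of examination at each time point is explicit. No SAP change is needed, since examination findings already enter as AEs. If the lighter schedule is intended, the protocol should say so and give the reason.

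Cost: three of ten planned examinations become somewhat longer and include a weight measurement. No visit or additional staff is needed. The flow chart change has to go into an amendment, which needs ethics and authority approval under Section 8.1, so it is best combined with the next one.

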## **ABBREVIATIONS**

ADA	Anti-Drug Antibody
AE	Adverse Event
AESI	Adverse Event of Special Interest
ALCOA	Attributable, Legible, Contemporaneous, Original, Accurate
ALT	Alanine Aminotransferase
AST	Aspartate Aminotransferase
AUC	Area under the Curve
BI	Boehringer Ingelheim
CA	Competent Authority
C max	Maximum Concentration
CMV	Cytomegalovirus
CRA	Clinical Research Associate
CRF	Case Report Form, paper or electronic (sometimes referred to as “eCRF”)
CRO	Contract Research Organisation
CT Leader	Clinical Trial Leader
CT Manager	Clinical Trial Manager
CTP	Clinical Trial Protocol
CTR	Clinical Trial Report
DILI	Drug Induced Liver Injury
DMC	Data Monitoring Committee
DSUR	Development Safety Update Report
EC	Ethics Committee
ECG	Electrocardiogram
eCRF	Electronic Case Report Form
EDC	Electronic Data Capture
EoS	End of Study
EoT	End of Treatment
EudraCT	European Clinical Trials Database
FAS	Full Analysis Set
FUP	Follow-up
GCP	Good Clinical Practice

GMP	Good Manufacturing Practice
HA	Health Authority
HBV	Hepatitis B Virus
HCV	Hepatitis C Virus
HIV	Human Immunodeficiency Virus
i.v.	intravenous
IB	Investigator's Brochure
ICH	International Council on Harmonisation
IEC	Independent Ethics Committee
IMP	Investigational Medicinal Product
IRB	Institutional Review Board
IRT	Interactive Response Technology
ISF	Investigator Site File
IUD	Intrauterine Device
IUS	Intrauterine Hormone-Releasing System
LPLT	Last Patient Last Treatment
LPLV	Last Patient Last Visit
MedDRA	Medical Dictionary for Drug Regulatory Activities
MRD	Multiple Rising Dose
Nab	Neutralizing Antibody
OPU	Operative Unit
PFS	Pre-filled syringe
PK	Pharmacokinetics
PRO	Patient Reported Outcome
PVAN	Polyomavirus nephropathy
RA	Regulatory Authority
REP	Residual Effect Period
s.c.	subcutaneous
SAE	Serious Adverse Event
(S)AE	(Serious) Adverse Event – refers to both serious and non-serious AE
SOP	Standard Operating Procedure
SRD	Single Rising Dose
SUSAR	Suspected Unexpected Serious Adverse Reactions

TB	Tuberculosis
TSAP	Trial Statistical Analysis Plan
ULN	Upper Level of Normal
WHO	World Health Organisation
WOCBP	Woman of childbearing potential

